Furthermore, breast cancer intrinsic subtypes, as evaluated by PAM50 transcriptomic profiles, were observed to differently benefit from CDK4/6i in combination with ET. In particular, basal-like tumors are associated with poor prognosis and refractoriness to the addition of CDK4/6i to ET alone, as observed in a retrospective pooled analysis across the MONALEESA phase III studies (mPFS 3.7 with ribociclib vs 3.6 with placebo).^{32,33}

Prognostic biomarkers in HR+/HER2- aBC patients treated with first-line CDK4/6i plus ET combinations

Despite the tremendous improvement in the prognosis of HR+/HER2- aBC patients, a minority (~10-15%) of patients treated with first-line ET+CDK4/6i still undergo early disease progression. This subgroup of patients could therefore benefit from treatment intensification, such as through the addition of a target therapy (e.g., PI3Ki, AKTi, mTORi, PARPi for selected populations), hormonal backbone enhancement (e.g., oral SERD), or even from the use of a completely different treatment strategy such as chemotherapy or novel antibody drug conjugates (ADCs). Conversely, another subgroup of patients demonstrated to derive long-term benefit from ET+CDK4/6i in pivotal trials, with 23.3% of patients enrolled in the MONARCH 3 trial still on treatment after a median follow up of 72 months. These patients could potentially benefit from tailoring treatment in terms of de-escalation, sparing unnecessary toxicities without negatively impacting on survival outcomes.

However, there are no studies conducted to date with the specific aim of identifying the subset of patients at high risk of early progression or, conversely, long-term benefit. Several clinical and biological factors demonstrated in clinical trials to have relevant impact on prognosis, and the addition of specific CDK4/6i differently improved prognosis across pivotal trials. Among these, endocrine resistance, presence of liver metastasis, tumor biology intended as luminal A- or B-like disease, menopausal status, de novo metastatic presentation, patient age and comorbidity.^{37–40} Mason et al conducted an individual-level analysis using

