- Electrocardiographic parameters, in particular specific conduction alterations or arrhythmias and QTc value according to Fridericia, collected at baseline, after 15 and after 30 days from start;
- Patient comorbidity, understood as concomitant disease at the start of treatment with CDK4/6i ascertained by the physician and classified in macro-areas (e.g. cardiological, respiratory, metabolic, infectious, chronic diseases such as diabetes mellitus type 2);
- Concomitant therapies, initiated and ongoing before the start of treatment with CDK4/6i, reported as drug classes (e.g. steroid therapy, antibiotic therapy, proton pump inhibitors);
- Blood glucose and body mass index at baseline of CDK4/6i treatment.

(3) Medical imaging sub-study

Objectives and endpoints of the sub-study

Primary objective:

- To build a model able to predict prognosis of HR+/HER2- aBC patients treated with first-line ET+CDK4/6i using radiomics features extracted from baseline radiological images;
- To build a model able to predict prognosis of HR+/HER2- aBC patients treated with first-line ET+CDK4/6i using radiomics features extracted from baseline radiological images;
- To combine radiomics and pathomics features with clinical data to build a model able to predict prognosis of HR+/HER2- aBC patients treated with first-line ET+CDK4/6i;

Secondary objectives:

- To combine radiomics features with clinical data, pathomics, genomics and transcriptomics features to build a model able to predict prognosis of HR+/HER2- aBC patients treated with first-line ET+CDK4/6i;
- To build a model able to classificate HR+/HER2- aBC patients treated with first-line ET+CDK4/6i in early and late progressors using radiomics features extracted from baseline radiological images;
- To build a model able to predict prognosis of HR+/HER2- aBC patients treated with first-line ET+CDK4/6i using baseline radiomics features and early radiomics modifications detected from first on-treatment radiological evaluation;
- To build a model able to predict molecular characteristics, such as *PIK3CA* and *ESR1* mutational status, of HR+/HER2- aBC patients treated with first-line ET+CDK4/6i using radiomics features extracted from baseline radiological images;
- To build a model able to predict molecular characteristics, such as *PIK3CA* and *ESR1* mutational status, of HR+/HER2- aBC patients treated with first-line ET+CDK4/6i using radiomics features extracted from digitalized HE slides;

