A team of four radiologists with experience on CT scan/PET images segmentation will identify the Volume Of Interest (VOI) through a semi-automated 3D segmentation process performed with Syngo.via software. An ad hoc designed segmentation protocol will be applied to homogenize the choice of CT/PET sequence on which to perform segmentation and the choice of the lesion to be segmented. Peritumoral area will be obtained through automated augmentation techniques (+5 mm, +10 and +15 mm); if the peritumoral area obtained crosses blood vessels, gas, bone, bile duct, or exceeded the organ edge, the contour will be manually modified to exclude this area. After image pre-processing through different techniques (e.g., gray discretization, intensity normalization, and voxel resampling), radiomic features will be extracted from VOIs and peritumoral areas using the PyRadiomics library in Python. In order to prevent signature overfitting, dimensionality of features is reduced before signature construction, firstly excluding features with high intraclass correlation coefficient and significantly different between the two outcome groups as assessed by one-way analysis of variance (ANOVA). Least absolute shrinkage and selection operator (LASSO) regression and/or Maximum Relevance Minimum Redundancy (MRMR) will be then used for the selection of features that will be included in the final model. The cohort will be split in a training (80%) and testing cohort (20%). Different standard classifiers, such as Random Forest, Multilayer perceptron, Logistic

Regression, Support Vector Machine, CatBoost, AdaBoost, XGBoost, will be trained and evaluated for this task. 91,92

Pathomics Methodology

Pathology slides will be digitalized with Leica Scanscope AT2 and stored as ".svs" files to obtain Whole Slide Images (WSIs). Hematoxilin and Eosin (HE) slides will be digitalized for pathomics purposes. WSIs will be analysed through Slideflow, a Python package that provides a unified Application Programming Interface for building and testing models for histopathology. After color normalization procedures, quantitative pathomics features will be extracted. Model creation and performance evaluation will follow the same methodology discussed in the "Radiomics" workflow. 93

Multimodal integration

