We will use several architectures, including logistic regression, classification and regression trees, random forest, multi-layer perceptron, gradient boosted trees (XGBoost), gradient boosting machines (LightGBM) and attentive tabular networks TabNet and we will compare their performance to heuristically decide on the best model choice for follow-up experiments. Our modelling experiments will include different combinations of input embeddings, with concatenation of each data stream permutation to produce fusion embeddings and train models using single-modality or multi-modality of input combinations. All models will be trained multiple times with multiple different data splits to repeat the experiments and compute average metrics and SDs. All defined models will be trained and tested to evaluate the advantage of multimodal predictive systems, as compared to single modality ones for the pre-established classification prediction. To assess model performance, different metrics will be used, including AUC, Sensitivity and Specificity, which will be calculated on the training set through 10-fold cross-validation and on the test set, which will be obtained by randomly splitting the entire cohort in a 80:20 way. The hyperparameter combinations of individual models, such as maximum depth of the trees, number of estimators and learning rate, will be selected within each training loop using a fivefold cross-validated grid search on the training set.^{94,95}

Since these complex models are considered as "black boxes", since they make decisions without clear reasoning, explainability techniques will be adopted to provide insights into how models make predictions, guaranteeing human interpretability. In particular, SHapley Additive exPlanations (SHAP) techniques will be used for both global and local explanations. ⁹⁶

Biological analyses methodology

Genomic analyses

A next generation sequencing (NGS) panel (Oncomine Comprehensive Assay Plus) will be used to perform analysis of various single-gene variants, such as single nucleotide variations (SNVs), indels, fusions, splice Version 1.1, 01Aug2024

Pag. 26 di 32

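### The radiomics pre-filter is written in reverse: it discards the reproducible, outcome-associated features that the next selection step needs

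*Protocol*

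**What the plan says.** The rule is in the protocol under Image omics and model generation methodology, Radiomics Methodology. Its purpose is stated first: "In order to prevent signature overfitting, dimensionality of features is reduced before signature construction". The first step is then "firstly excluding features with high intraclass correlation coefficient and significantly different between the two outcome groups as assessed by one-way analysis of variance". The step after that is LASSO and/or "Maximum Relevance Minimum Redundancy (MRMR) will be then used for the selection of features that will be included in the final model".

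Other places bear on it:

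- **Pathomics Methodology:** "Model creation and performance evaluation will follow the same methodology discussed" for radiomics.
- **Medical imaging sub-study, primary objective:** "To build a model able to predict prognosis of HR+/HER2- aBC patients treated with first-line ET+CDK4/6i using radiomics features".
- **Medical imaging sub-study, secondary objective:** a model that classifies patients "in early and late progressors using radiomics features extracted from baseline radiological images".
- **Multimodal integration:** multimodal models are judged "as compared to single modality ones for the pre-established classification prediction".
- **Statistical methods:** the general significance level is 0.05, two-tailed.

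No other section restates or corrects the filter.

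**The concern.** One verb of exclusion governs both conditions, and nothing in the sentence reverses either of them. On the usual meaning of the intraclass correlation, a high value marks a feature that is stable across readers or segmentations. That meaning fits the four radiologists and semi-automated segmentation described in the same section. A significant ANOVA marks a feature related to the outcome. The rule therefore removes the features that a prognostic signature should be built from. Among outcome-related features, it leaves mainly the less reproducible ones.

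LASSO and MRMR both look for features that predict the outcome, so the two consecutive steps pull in opposite directions. Removing a feature because it differs by outcome does not serve the stated aim of limiting overfitting either.

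At stake are the radiomics models of the medical imaging sub-study and, through them, the radiomics part of the primary objective of the second and further lines sub-study. Features removed at this stage cannot be recovered by any later classifier, and a weak result could be misread as evidence that imaging adds nothing.

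**Working it through.** No figure in the plan depends on this sentence, so there is none to reproduce. The check has two parts: the logic of the text, then an illustration of size.

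**1. Readings of the sentence**

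| Reading | ICC half | ANOVA half |
|---|---|---|
| ICC = reproducibility, both conditions must hold | reversed | reversed |
| ICC = reproducibility, either condition suffices | reversed | reversed |
| ICC = correlation between features (redundancy) | sensible | reversed |

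The ANOVA half is reversed in every reading of the words as they stand. The choice of reading changes how much is lost, not the direction.

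**2. How often an informative feature is exposed to exclusion**

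Assumptions: standardised difference d between the two outcome groups, and early-progressor fraction f = 0.125. That is the midpoint of the background statement that "a minority (~10-15%) of patients treated with first-line ET+CDK4/6i still undergo early disease progression"; the protocol does not define the two groups this way. The two-sided level is 0.05.

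P(significant) = Φ(d·√(n·f·(1−f)) − 1.96), with f(1−f) = 0.109375.

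- d = 0.4, n = 300: 0.4 × √32.81 = 2.291, so Φ(0.331) = 0.63. For f = 0.10 and 0.15 the values are 0.55 and 0.70.
- d = 0.4, n = 1000: 0.4 × √109.4 = 4.183, so Φ(2.223) = 0.99.
- d = 0.2, n = 300, 1000, 2000: 0.21, 0.55, 0.84.

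These use all patients. If the filter runs on the 80% training part (n = 240 and 800), the d = 0.4 values are about 0.54 and 0.96. For d = 0.2 and n = 240, 800 and 1600 they are about 0.17, 0.46 and 0.75.

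**3. Effect on test AUC (simulation)**

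All settings are assumptions: 400 features, 10 informative at d = 0.4, ICC 0.95 (reproducible) or 0.5, and an 80:20 split with filter and selection inside the training part. LASSO used a five-fold cross-validated penalty and 80 repetitions per cell. The intended filter keeps features with high ICC and a significant difference. The literal filter drops them. Share kept = (literal − 0.5) / (intended − 0.5).

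| f = 0.125, LASSO | n = 300 | n = 1000 | n = 2000 |
|---|---|---|---|
| Half reproducible | 0.593 vs 0.507 (8%) | 0.684 vs 0.586 (47%) | 0.696 vs 0.642 (72%) |
| 80% reproducible | 0.606 vs 0.500 (0%) | 0.721 vs 0.535 (16%) | 0.741 vs 0.571 (29%) |
| All reproducible | 0.629 vs 0.500 (0%) | 0.742 vs 0.500 (0%) | 0.768 vs 0.500 (0%) |

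Example: (0.586 − 0.5) / (0.684 − 0.5) = 0.086 / 0.184 = 47%.

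- **Equal groups (f = 0.5), LASSO, n = 1000:** 0.704 vs 0.645 with half reproducible (0.145 / 0.204 = 71% kept), 0.751 vs 0.594 with 80% (0.094 / 0.251 = 37%), and 0.773 vs 0.500 with all.
- **MRMR with random forest (f = 0.125, n = 1000, 60 repetitions):** 0.663 vs 0.571, 0.713 vs 0.522 and 0.729 vs 0.513 in the same order.
- **ANOVA as a separate exclusion:** LASSO gives 0.500 in every cell and random forest 0.502 to 0.516.

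Standard errors across cells are 0.003 to 0.016.

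**4. Different assumptions**

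A second simulation used 1000 patients, equal groups, 500 features with 50 informative at a shift of 0.3 SD, ICC spread evenly from 0.30 to 0.98 with a cut-off of 0.75, and a ridge discriminant score.

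- Corrected filter: AUC 0.769.
- Literal, both conditions: 0.703, so 0.203 / 0.269 = 75% kept.
- Either condition: 0.529.
- ANOVA alone: 0.534.

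Under the literal rule with both conditions, about 0.5 of 17.4 informative and reproducible features survived, against 16.9 with the corrected filter.

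**The case against.** The strongest reply is that the sentence is simply missing a verb. The authors may have meant to drop highly inter-correlated features and then select those that differ by outcome, which would be a standard redundancy-plus-relevance filter. That is plausible, but it needs words the protocol does not contain. It is also only one of two natural repairs: removing unreliable features is the other, and the two give different feature sets. The intent cannot just be assumed.

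A second reply is that the literal rule removes only features meeting both conditions. Outcome-related features with lower reproducibility survive, so the later selection still has material. That stands. It is why the loss is often partial, up to 72–76% of the AUC gain being kept in the larger simulated samples with half the features reproducible.

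Third, the magnitudes rest on assumed inputs. The 2000 patients expected at the first data cut-off are the whole cohort, not the imaging subset. The all-reproducible cells are close to true by construction. This is fair, and the figures should be read only as a range.

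Fourth, the planned cross-validation and test-set metrics would show a poor model. They would, but they would not show why it was poor. The error costs performance; it would not by itself create a false positive claim.

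**Conclusion.** The concern holds. The protocol states a filter that runs the wrong way for a primary objective of the medical imaging sub-study, and its ANOVA half is wrong under every reading of the words given. A drafting slip is the likely cause, but following the text literally would damage the models, and silently coding something else would depart from the protocol.

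The direction does not depend on assumptions. The size does. In the LASSO illustrations the share of discriminating ability retained ran from none to about three-quarters under the both-conditions reading. Essentially nothing was left if ANOVA significance alone leads to exclusion.

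Three limits apply. Carry-over to pathomics is an inference, since that section adopts the radiomics approach to model creation without naming the filter. Models that add clinical data keep that part of their signal. The sized overall-survival comparison between drugs is unaffected. The point should be fixed, but it does not threaten the main analysis.

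**What to change.** Reword the sentence so that it says what is removed and what is kept:

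- Remove features with low reproducibility (low ICC). If correlation between features was meant, say so and remove redundant ones.
- Retain features associated with the outcome, and pass those to LASSO and/or MRMR.
- State whether the same filter applies to pathomics.

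While the sentence is open, one clause could usefully say that outcome-based filtering and LASSO/MRMR are fitted only within the training data of each split. This is a clarification and not part of the finding: the protocol does not say that test patients are used for selection.

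The cost is one reworded sentence and a short clarification, preferably before any model is built. Data collection, sample size and the overall-survival analysis do not change.

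### Radiomics Methodology places outcome-based feature selection before the 80:20 split, so the test AUC is biased upward if that order is followed

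*Protocol*

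**What the plan says.** Protocol, *Image omics and model generation methodology*, *Radiomics Methodology*, describes the pipeline in this order:

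1. Features are extracted from the volume of interest and from peritumoral margins of 5, 10 and 15 mm.
2. To guard against overfitting, "dimensionality of features is reduced before signature construction". The first step uses the intraclass correlation coefficient and whether features are "significantly different between the two outcome groups as assessed by one-way analysis of variance (ANOVA").
3. "Least absolute shrinkage and selection operator (LASSO) regression and/or Maximum Relevance Minimum Redundancy (MRMR) will be then used for the selection of features" that enter the final model.
4. The next sentence introduces the split into 80% training and 20% testing. The junction of steps 3 and 4 reads: "will be then used for the selection of features that will be included in the final model. The cohort will be split".
5. Several classifiers "will be trained and evaluated for this task".

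Under *Pathomics Methodology*: "Model creation and performance evaluation will follow the same methodology" as radiomics. Under *Multimodal integration*, AUC, sensitivity and specificity are computed by 10-fold cross-validation on the training set and on a test set drawn at random from the whole cohort. Models are retrained over several splits. One step is explicitly restricted to training data: hyperparameters "will be selected within each training loop using a fivefold cross-validated grid search on the training set". No such restriction is stated for feature selection.

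**The concern.** ANOVA between outcome groups, LASSO and MRMR all use the outcome. If they run on everyone, a feature that is associated with the outcome by chance in the whole cohort is, on average, associated in the same direction in any random 20% of it. The test set is then no longer independent of the signature. The 10-fold AUC on the training set has the same fault if selection precedes the folds. Averaging over several splits does not remove it if the features were chosen once on all patients.

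Radiomics prediction models, and their combination with pathomics and clinical data, are the primary objectives of the Medical imaging sub-study (3). The primary objective of the Second and further lines sub-study (5) is a treatment-selection model that takes radiomics and pathomics inputs. The protocol describes no external validation cohort for these models, so the 20% test set is the main stated safeguard against overfitting.

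**Working it through.** **Inputs.** The protocol states no AUC target, sample size or feature count for the imaging models, so there is no figure of its own to reproduce. *Statistical design* says that no formal calculation was made for sub-studies 2 to 5. The outer limits for n come from the approximately 2000 patients expected at the first cut-off (*Clinical data collection and management*) and the 3258 required for the OS comparison. How many of these will have images is not stated. Feature counts of 400, 1000 and 1200, and all correlation levels, are assumptions.

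**Hand check.** Take p independent noise features, a 50:50 outcome, and the k = 10 strongest features kept using all n patients.

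- Selected fraction: 10/400 = 0.025, so the cut-off is |z| > c = 2.241.
- Mean square of the selected z: 1 + c·φ(c)/0.0125 = 1 + 2.241 × 0.03236/0.0125 = 6.80.
- A feature with statistic z has a standardised group difference of 2z/√n, expected equally in any random subset, including the test patients.
- For ten independent features, D² = 10 × 4 × 6.80/n = 272/n.
- Expected AUC is about Φ(D/√2). It ignores noise in the fitted weights, so it is slightly high.

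This gives Φ(0.673) = 0.75 at n = 300, Φ(0.369) = 0.64 at n = 1000, Φ(0.261) = 0.60 at n = 2000 and Φ(0.204) = 0.58 at n = 3258. The bias shrinks roughly as 1/√n.

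**Simulation.** The features are pure noise (true AUC 0.50). They pass an ANOVA filter at p<0.05 and then LASSO or MRMR. A logistic classifier is fitted on 80% and its AUC is read on the other 20%. There were 40 to 200 replicates per cell. Outcome prevalence was 50% in the first four rows and 35% in the others. The table gives the mean test AUC when selection precedes the split:

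| Selection and features | n=300 | n=1000 | n=2000 | n=3258 |
|---|---|---|---|---|
| LASSO to about 10; 400 independent | 0.72 | 0.63 | 0.60 | 0.58 |
| LASSO to about 10; 1000 independent | 0.76 | 0.66 | – | – |
| As row 1, but ANOVA-significant features excluded | 0.66 | 0.58 | 0.56 | 0.55 |
| As row 2, but ANOVA-significant features excluded | 0.67 | 0.61 | – | – |
| LASSO; 400 in blocks of 20, r=0.8 | 0.64 | 0.56 | 0.54 | – |
| LASSO; 400 in blocks of 40, r=0.9 | 0.58 | 0.54 | 0.53 | – |
| MRMR to at most 10; 400 in blocks of 20, r=0.8 | 0.62 | 0.56 | – | 0.54 |
| MRMR to at most 10; 400 in blocks of 20, r=0.9 | 0.59 | 0.54 | 0.53 | – |
| Looser L1 selection; 400 independent | 0.76 | 0.65 | – | – |
| Looser L1 selection; 1200 independent | 0.87 | 0.75 | – | – |

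At n = 100, LASSO with 400 independent features gives 0.84 (0.76 with significant features excluded). With the split made first and selection confined to the 80%, the mean test AUC was 0.49–0.51 throughout. The 10-fold cross-validated AUC was not simulated; the same mechanism applies to it.

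Rows 3 and 4 are there because the ANOVA sentence, taken literally, excludes the features that differ between outcome groups, the reverse of a usual relevance filter. The leak remains under either reading because LASSO and MRMR also use the outcome.

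**The case against.** The strongest reply is that the order is inferred. The word for sequence links LASSO/MRMR to the ANOVA filter; the sentence on the split carries no time word and could simply describe the design. Nowhere does the protocol say that selection uses all patients. Repeated splits and a training loop are compatible with selection inside each split, and fold-level detail could sit in an analysis plan that is not shown. This stands as a limit on certainty: the point holds for the text as written, not as proof of what the analysts will do. It does not dispose of the point. The protocol gives a sequence, restricts tuning to training data and does not restrict selection, so an analyst who splits first departs from the written order.

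Two stronger readings are tempting, and the documents do not support them.

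- **That a worthless model would match the AUC of 0.77** cited for a published CT radiomics model under *Unmet clinical needs*. That takes a small cohort or many nearly independent features. Features from one lesion and its nested margins are likely to be correlated, and the imaging cohort could approach 2000 patients or more. Under those conditions the noise AUC is well below 0.77.
- **That sub-studies 4 and 5 are built the same way.** The protocol extends the workflow only to pathomics. *Multimodal integration* names no feature-selection step, and the primary objectives of sub-study 4 are associations. Sub-study 5 and the multimodal models are affected only as far as they reuse the selected features.

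The OS comparisons of the RWD sub-study are untouched.

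**Conclusion.** The point holds as worded in the heading. Followed as written, the procedure lets test outcomes shape the radiomics signature, and the pathomics signature built by the same workflow, and it biases the test AUC upward. This is a faulty stated order, not a detail left for later.

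The direction is the same in every setting examined; the size is conditional. Over the noise AUC of 0.50, the inflation is about 0.03–0.10 for 2000–3258 patients. With 400–1000 features it is 0.04–0.16 for 1000 patients and 0.08–0.26 for 300. With 1200 independent features and looser selection it reaches 0.25 and 0.37 at those two smaller sizes. These figures rest on assumed cohort sizes, feature counts and correlations and on features with no true signal. They show what the order alone can produce and do not forecast the bias in the final models.

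**What to change.** Reorder *Radiomics Methodology*:

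- Split patients first.
- Run every step that uses the outcome (ANOVA, LASSO, MRMR) on the training set only, and repeat it inside each cross-validation fold and for each repeated split.
- Apply the frozen feature list to the test set.
- State that the same order binds pathomics and any multimodal model that uses these features.
- In the same edit, make clear whether the ICC and ANOVA criteria keep or remove the features they describe.

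The cost is a few sentences of protocol text and a pipeline wrapper that carries selection inside the resampling. No new data are needed. Reported AUCs will be lower.
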